**6) Can data be modified or updated after an assessment is entered as complete?**

An assessment is considered complete when the radiologist enters their initials into the data form. Data can be modified or updated until the nighttime process determines adjudication is needed. If adjudication is needed, the original records are locked, and updates or modification can then only be made through the adjudicated records (DM3, VR3, and UR3).

[figure not shown]

### Appendix 3.3: Zipping and Encrypting with Winzip Pro 11.2 for CUTIE Study

[figure not shown]
Insert radiology cd into your computer.

Open "My computer" from the Start Menu

[figure not shown]

### Appendix 3.3: Zipping and Encrypting with Winzip Pro 11.2 for CUTIE Study

[figure not shown]

Click on the edit menu and select "Select all" so that the files on the CD are highlighted

### Appendix 3.3: Zipping and Encrypting with Winzip Pro 11.2 for CUTIE Study

[figure not shown]

Right click on the selected files and select Winzip -> "Add to Zip"

[figure not shown]

Click on "Desktop" on the left and then name your file: USERID\_CO\_SQ\_Type where: Co= Contact Occasion, SQ = Sequel Number, and Type = VCUG, ULTRA or if both VCUG\_ULTRA – Click OK once file is named.

[figure not shown]
### Appendix 3.3: Zipping and Encrypting with Winzip Pro 11.2 for CUTIE Study

Select "Encrypt added files" then click "ADD" in upper right

[figure not shown]

### Appendix 3.3: Zipping and Encrypting with Winzip Pro 11.2 for CUTIE Study

Enter password that is provided by DCC **\*\*DO NOT MAKE UP YOUR OWN PASSWORD!!\*** [IMPORTANT: 256-Bit encryption should already be selected] then click OK – The program will then create the zip file. Once it is finished remove your radiology cd and insert a BLANK CD

[figure not shown]
[Allow time for processing, could take a minute or so]

From the File menu select Send to-> CD or DVD

### Appendix 3.3: Zipping and Encrypting with Winzip Pro 11.2 for CUTIE Study

Select the the CD or DVD drive letter that corresponds to your drive. Click OK  
[Allow time for processing. Could take a couple of minutes to write each CD.]

[figure not shown]
The CD will burn and then you can remove it once it's finished. Then label and ship it according to CUTIE protocol.

Once all CDs have been burned, delete the zip file from the desktop.

If you have any questions please call the DCC at [name].

### Appendix 3.4: Extracting Zip Files with Winzip Pro 11.2 for CUTIE Study

[figure not shown]
Insert the cd into your computer.

[figure not shown]
Open your CD drive from the My computer menu.

Right click on the zip file on the CD and select Winzip -> "Extract to"

### Appendix 3.4: Extracting Zip Files with Winzip Pro 11.2 for CUTIE Study

[figure not shown]

Select where you would like to extract the files to. To create a new folder select the folder icon from upper right (red circle). Click "Extract"

[figure not shown]

The files will be extracted to the location you specified and ready to be read.

**If you have any questions please call the DCC at [name].**

Select where you would like to extract the files to. To create a new folder select the folder icon from upper right (red circle). Click "Extract".

The files will be extracted to the location you specified and ready to be read.

If you have any questions please call the DCC at [name].

# Chapter 4: Enrollment and Baseline

## 4.1 Overview

The goal of recruitment and eligibility determination is to enroll eligible children as quickly and efficiently as possible for inclusion into the study. The overall goal of CUTIE is to enroll 360 children (180 per arm) over a 24-month recruitment period.

This chapter describes the procedures, data collection forms, and the ordering of procedures and data collection that must be followed for enrollment and baseline data collection.

## 4.2 Prior to the Enrollment Visit

### 4.2.1 Initial screening and Informed Consent (ICT)

Prior to enrollment, all potential participants must be initially screened, have local renal ultrasound and VCUG results (with images and VCUG sedation information), and been appropriately treated for their first or second F/S UTI.

Informed consent procedures must be completed with the child's parents or legal guardian prior to enrollment.

Refer to Chapter 2: Recruitment, Screening and Eligibility for full details on eligibility, inclusion and exclusion criteria, and the process of informed consent.

### 4.2.2 Modification of Informed Consent

A participant may modify their Informed Consent at any time during the study. If a participant indicates a change in their consent to participate in the study, complete another Informed Consent Tracking Form (ICT).

## 4.3 Enrollment and Baseline Components

The primary objective of the baseline visit is to re-confirm eligibility and obtain baseline information and specimens. The baseline visit is composed of the following parts:

- 1) Re-assessment of all inclusion and exclusion criteria
- 2) Enrollment using the web-based DMS during entry of the EEF forms
- 3) A brief physical examination
- 4) Collection of participant demographic characteristics and medical history
- 5) Collection of concomitant medication data
- 6) Collection of baseline blood and urine
- 7) Parental completion of the self-administered questionnaires

### 4.3.1 Data Collection Forms

The data collection forms required to complete the baseline visit are the listed below in Table 4.1.

**Table 4.1 Baseline Data Collection Forms**

**Forms Collected Prior to Enrollment:**

- Informed Consent Tracking Form (ICT)
- VCUG Sedation Form (VSF)

**Forms Collected During Baseline Contact:**

- Eligibility and Enrollment Form (EEF)
- Baseline Demographic Form (BDF)
- Physical Exam Form (PEF)
- Baseline Medical History Form (BMH)
- Concomitant Medication Listing/Coding Form (CMF)
- LIA (Life Impact Assessment) Questionnaire (LIQ)
- Dysfunctional Voiding Questionnaire (DVQ) – if toilet trained
- Specimen Collection Form (SCF)
- Participant Contact Form (PCF) \*
- Biospecimen Repository Shipping Log (NIDDK-USL) \*
- Genetics Repository Shipping Log (NIDDK-BSL) \*
- VCUG / Ultrasound Inventory and Shipping Log (VUS)

**Forms Completed after the Baseline Visit (though still contact occasion = 01)**

- Blood Specimen Results Form (BSR)
- Urine Specimen Results Form (USR)
- DMSA Sedation Form (DSF), unless collected prior to baseline
- DMSA Imaging Inventory and Shipping Log (DSS)

**Reference Radiologist Forms (completed and entered by the radiologists)**

- Ultrasound Results Form (URF)
- VCUG Results Form (VRF)
- DMSA Results Form (DMF)

\* Not data entered

### 4.3.2 Ordering of Data Collection during the Visit

Sites may organize the Baseline data collection to accommodate their own staffing and organization needs. There are, however, a few things that are required and need to be considered:

1. Consent must be obtained and the ICT entered prior to any study data collection or enrollment.
2. A urine dipstick negative for pyuria is required prior to enrollment to assure no new infection is present. If pyuria is positive on dipstick (leukocyte esterase  $\geq$  trace), a

negative WBC (**WBC < 10 WBC/mm^3 or WBC < 5 WBC/hpf**) obtained on this same urine may trump the dipstick to document absence of pyuria. At this same time, urine for local chemistries (creatinine and microalbumin) and repository storage should also be collected.

3. Weight measurement during the physical exam must have been taken prior to blood specimen collection.

#### **4.3.3 Data Entry during Visit**

CUTIE data collection can be recorded on paper data collection forms, or entered directly online into the CUTIE data management system (DMS). Four forms are required to be entered at the enrollment/baseline visit: the ICT must be entered as documentation of participant consent, and the EEF must be entered to enroll the participant.

All other data collection forms can be entered after the clinic visit is completed. The DCC requires all data collection forms to be entered within 5 working days of data collection.

### **4.4 Enrollment**

The process of enrolling participants in CUTIE is the official confirmation of all eligibility criteria, and a final ruling out of potential exclusions.

In order to enroll a child, he or she **MUST** be present in the clinic. You cannot run the eligibility algorithm in the web-based data management system prior to the clinic visit.

#### **4.4.1 Verifying no new UTI prior to Enrollment**

Prior to enrollment, you must verify that the child has not experienced a temperature ( $\geq 100.4^{\circ}\text{F}$  or  $58^{\circ}\text{C}$ ) anytime in the last 24 hours; this could be done by a telephone call the day before the scheduled visit. If the child has been sick with fever, the Coordinator will need to verify that this is not another UTI. Enrollment must be rescheduled.

A urine dipstick test must also be performed and be negative for pyuria. In the event that the dipstick is positive for pyuria, that same urine may be spun and checked for the presence of WBC using microscopy. If pyuria is present, you must obtain catheterized urine specimen for culture to verify that the child does not currently have a UTI. This would require rescheduling of the enrollment and baseline data collection. If the urine culture results are negative, the child should be scheduled for enrollment. During the enrollment, the urine should be dipped for pyuria, but the child may be enrolled, even if pyuria is present at the second attempt of enrollment.

#### **4.4.2 Eligibility and Enrollment Form (EEF)**

Eligibility verification is completed upon data entry of the EEF form, at this enrollment visit. You may have used this form initially as a tool to pre-screen or screen the child for consideration. However, it is critical that this form is completed appropriately at **this** clinic

visit to officially verify all eligibility criteria. Some criteria may have changed since pre-screening and screening.

Particular attention must be made to accurately assess the number of UTI's that the child has experienced. The child is eligible for CUTIE if they have had 1 or 2 UTI's. In the event that more than one UTI has occurred, in order for the child to be eligible, he/she may not have been treated with prophylactic anti-microbials nor had a VUR diagnosis. The UTI immediately preceding the enrollment into CUTIE will be called the index UTI. You must have medical record documentation of the diagnosis of the index UTI, documentation of fever or symptoms occurring within  $\pm 24$  hours of the beginning of the index UTI workup, and documentation showing appropriate treatment for at least 7 days with an effective drug.

Refer to Chapter 2: Recruitment, Screening and Eligibility, and the EEF QXQ for specific details regarding eligibility and the EEF form.

At the time of enrollment, verify that the child is at least 2 months of age, and less than 72 months and the index UTI had occurred within 112 days of enrollment. All VCUG and U/S images must be collected prior to enrollment, must also have been collected after the index UTI and within the 112 days of the enrollment date. The baseline DMSA must be collected within 2 weeks of enrollment and no more than 112 days from the index UTI.

#### **4.4.3 The Enrollment Procedure**

Enrollment occurs during the data entry process of the EEF form.

Refer to Chapter 2: Recruitment, Screening, and Eligibility for specific details on eligibility and the EEF form.

##### **4.4.3.1 Enrollment Procedure Using the Data Management System**

The Coordinator enters the data from the EEF into the DMS. As the EEF form is data entered, the DMS will validate all responses. If an edit fails, the DMS will provide an automatic query message and skip the entry to the end of the form, bypassing the enrollment. If all edits pass, the form asks "Do you wish to enroll this child into the CUTIE Study?" Entering a "Y" in this field enrolls the child.

The eligibility/enrollment program verifies the patient's eligibility status based on the entered responses. At this time the system will let you know that the enrollment was successful..A successful enrollment will automatically send an email to the DCC notifying them of the enrollment.

In the event that the enrollment program aborts and does not run, you will receive an error message explaining the reason for the random information in the EEF. Make the necessary corrections to the EEF begin the enrollment procedure again.

#### 4.4.3.2 Enrollment when the Data Management System is Not Functional

Since the enrollment procedure requires entry through an internet connection, a backup procedure is necessary for cases in which the clinic's computer system is not functional, or the WEB is inaccessible or not operating appropriately.

As soon as it is realized that an enrollment is anticipated and the DMS is nonfunctional, contact the DCC to arrange a remote enrollment. Emergency enrollment procedures will be done over the phone with the DCC.

- All necessary data collection forms must be completed on paper.
- The Eligibility and Enrollment Form (EEF) must be completed to provide final assessment, verification, and review of enrollment eligibility.
- The Physical Exam Form (PEF) must be completed to provide the weight measurement for dosing.
- The Study Coordinator (or other appropriately trained staff member) can call the DCC at [contact], normally staffed from 8AM – 5PM EST, Monday through Friday. Enrollments at other times must be arranged in advance.
- The DCC must receive faxed copies of completed EEF and PEF data collection forms prior to the enrollment call.
- Participant baseline data collection can be ongoing while the process of emergency enrollment is being completed.

First, the DCC will attempt to solve the computer problem, if it relates to the CUTIE DMS. If this fails, the Study Coordinator and the DCC will review the participant's eligibility forms over the phone, and obtain the participant's weight. The DCC will then enroll the participant. (Note: Since chances for error are increased by transmitting eligibility data over the phone, this system should only be used when absolutely necessary.)

As soon as the system at the clinical center becomes operational, entry of the EEF and PEF must be completed in the DMS system BEFORE ANY FURTHER ENROLLMENTS CAN OCCUR, and the contact person providing the phone enrollment must be notified that this has happened. It is essential to enter any remote enrollments into the CUTIE DMS in the order in which they were enrolled by phone, before using it for any further enrollments.

## 4.5 Baseline Data Collection

Baseline data is collected in order to adequately describe the population in the trial. This includes demographic variables of gender, ethnicity and race, and includes socio-economic factors such as income and education. Some baseline data includes collecting known factors that may influence the outcome, such as concomitant medications being taken by participants, and medical history information.

Baseline data collection can be obtained in any order that is efficient at the clinical sites. Except for urine collection (required for final eligibility assessments) it is recommended that

the blood specimens not be collected prior to enrollment. Any baseline data collected prior to enrollment will have to be repeated if the enrollment is rescheduled.

#### **4.5.1 Physical Exam (PEF)**

The physical exam includes temperature, blood pressure, height and weight measures as well as a short abdominal exam, all reported on the Physical Exam Form (PEF). The weight measurement taken during the physical exam will be used to assess the amount of blood drawn for laboratory specimens.

Refer to the PEF QxQ for item-specific instructions regarding administration.

#### **4.5.2 Baseline Data Collection Interviews**

Much of the baseline data collection is done through interviewing the parent/guardian. Parent/Guardian interview forms include the Baseline Demographic Form (BDF), the Baseline Medical History Form (BMH) and the Concomitant Medication Form (CMF).

Section 13.9 of Chapter 13: Data Management and Administrative Procedures, includes techniques for conducting questionnaire interviews.

Refer to the QxQ documents for the BDF, BMH, and CMF for item specific instructions regarding administration.

##### **4.5.2.1 Concomitant Medication Form (CMF)**

Concomitant medications are often collected on patients involved in a research study. This data is collected based on parent/guardian's report. Parents will be requested to bring in medication bottles of any medications their child is currently, or has taken since the last contact, or to record and bring in this information in the Participant Handbook/Diary.

Of particular interest are anti-microbial medications in addition to any other prescription medications for chronic conditions, or medications for constipation or over-active bladder. At baseline, only those medications currently being taken and the prophylactic antimicrobial the child had been taking following his/her UTI diagnosis will be recorded along with the start dates for the medication(s). In the case of the antimicrobial prophylaxis taken prior to enrollment, the date the medication was completed will be the day of enrollment.

Concomitant medications are coded in order to summarize the data by a preferred term. Coding of concomitant medications is assigned into the DMS at the time of CMF data entry, using a drug dictionary lookup table in the DMS. The CMF form will be data entered at every CUTIE protocol-scheduled contact.

Refer to the CMF QxQ for more instructions on reporting concomitant medications including instructions on coding a stop date for continuing medications, and Chapter 14: DMS User's Guide for information on coding.

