Prior studies designed to identify risk factors for renal scarring have had several significant limitations to their internal validity and generalizability. First, most studies had very small sample sizes (33-157; mean=89), significantly limiting their power to detect associations between risk factors and scarring. For example, assuming a study enrolled 100 subjects, one-third of whom had the risk factor of interest, and the rate of scarring in the group without the risk factor was 10%, the study would have only enough power to detect an odds ratio (OR) of 5.1 for that risk factor (assuming power=80% and alpha=0.05). Starting out with fewer subjects (as was the case with 2 of the 3 prior studies) and a lower rate of scarring in the unexposed group (subjects who do not have the risk factor) would increase the smallest detectable OR even further. In other words, only risk factors that were very strongly associated with renal scarring would have been detectable in these studies. The second limitation of prior studies is that they generally sought to determine the predictive value of one, or at most two, risk factors for renal scarring and did not employ multivariable models to increase the explanatory power of several factors associated with that outcome. By increasing the sample size and including factors that are even modestly associated with renal scarring, we expect to derive predictive models in the proposed study that have greater explanatory power. Prior studies have also included highly selected populations, for example exclusively hospitalized children or children with a history of multiple previous UTIs. By enrolling an inception cohort of children with their first or second documented UTI

and recruiting from primary care as well as sub-specialty and inpatient settings, we expect that our results will be more reflective of the overall population of children with UTIs and therefore more generalizable. Finally, but most importantly, prior studies have included children treated with prophylactic antimicrobials, which may have affected renal scarring rates. By combining data from placebo treated children in RIVUR who have VUR and untreated children in the proposed ancillary study who do not have VUR, we will have the unique, and perhaps only, opportunity to understand the risk factors for renal scarring after UTI in the absence of antimicrobial prophylaxis.

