#### **4.10 Subject Completion/Withdrawal**

Criteria for withdrawal of subjects and plans for provision of care after withdrawal. Example: Subjects may withdraw from the study at any time without prejudice to their care. They may also be discontinued from the study at the discretion of the Investigator for lack of adherence to study treatment or visit schedules or AEs. Children who are started on antimicrobial prophylaxis will continued to be followed for the duration of the study period but they will not contribute data to analyses after prophylaxis is begun. The Investigator may also withdraw subjects who violate the study plan, or to protect the subject for reasons of safety or for administrative reasons. It will be documented whether or not each subject completes the clinical study. If the Investigator becomes aware of any serious, related adverse events after the subject completes or withdraws from the study, they will be recorded in the source documents and on the CRF.

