#### **4.5.5 Medication Dispensing and Dosing Form (MDD, MDL)**

The CUTIE Study does not have any study medication.

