8. CONCOMITANT MEDICATION USE

4. Have there been any changes in the child's concomitant medication use since the last contact? (Y/N)  EEE

5. Medication:  AEE

Preferred name:  AEE

Date start:  AEE

Date stop:  EEE

6. Medication:  EEE

Preferred name:  EEE

Date start:  EEE

Date stop:  EEE

[figure not shown]
The AEF form has a similar look-up feature for coding Adverse Events.

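### MOP 4.5.2.1 fixes the stop date of pre-enrolment prophylaxis as the day of enrolment, although CUTIE has no study drug to replace it, so prophylaxis exposure may be misrecorded in either direction

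*Protocol*

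**What the plan says.** MOP 4.5.2.1 governs the Concomitant Medication Form (CMF). At baseline, "only those medications currently being taken and the prophylactic antimicrobial the child had been taking following his/her UTI diagnosis will be recorded", with start dates. It then sets the stop date by rule: "In the case of the antimicrobial prophylaxis taken prior to enrollment, the date the medication was completed will be the day of enrollment". No exception is made for a child who stopped earlier or who continues. The section adds that "The CMF form will be data entered at every CUTIE protocol-scheduled contact" and refers to the form's question-by-question guide (QxQ) for "instructions on coding a stop date for continuing medications". That guide is not part of the document at hand.

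MOP 4.5.5 states that "The CUTIE Study does not have any study medication"; MOP 8.3 says the same.

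Protocol 1.1.3 presents the CUTIE children as untreated and gives the aim of combining them with RIVUR placebo children as "to understand the risk factors for renal scarring after UTI in the absence of antimicrobial prophylaxis". Protocol 4.10 says that children who are started on prophylaxis stay in follow-up, but "they will not contribute data to analyses after prophylaxis is begun".

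The CMF screen reproduced in MOP 14.4.12 asks: "Have there been any changes in the child's concomitant medication use since the last contact".

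**The concern.** A stop date is a fact to be collected. In a randomised drug trial it can be set by design, because earlier prophylaxis ends when study drug begins. CUTIE is observational and dispenses nothing, so nothing makes the day of enrolment the true date. The opening statement of the document says that CUTIE materials were adapted from RIVUR with inapplicable parts crossed out. This sentence is not marked as struck out, and it reads as RIVUR text left in place, like the references to study medication that remain in MOP 7.4.6.1, 10.6 and 10.7.3.

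At stake is the exposure status on which the comparison rests. The RIVUR comparators are on placebo by assignment, whereas the CUTIE children are off prophylaxis only if the record shows it correctly. If the record is wrong, the untreated premise in 1.1.3 cannot be checked and the data rule in 4.10 cannot be applied as intended.

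**Working it through.** The point rests on wording, so the sections are compared first. A bounding calculation follows.

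**1. Can a child on prophylaxis enrol?** Protocol 3.3.1 and 3.3.2 and MOP Table 2.1 list no exclusion for prophylaxis after the index UTI. The bar in the index-UTI definition and in MOP 2.3.2.1 and 4.4.2 applies where there has been more than one UTI. A child with a first UTI is not barred, and MOP 4.5.2.1 itself expects some children to have taken prophylaxis after diagnosis.

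**2. Does anything end prophylaxis at enrolment?** No section does.

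**3. What does the rule then enter?**

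| True course | Date entered | Error |
|---|---|---|
| Stopped on the day of enrolment | Enrolment | None |
| Stopped earlier, for example after a negative VCUG | Enrolment | Exposure recorded as too long |
| Continues after enrolment | Enrolment | Follow-up recorded as unexposed |

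In the second row the error is limited. Enrolment is at most 112 days after the index UTI (3.3.2), and treatment of at least 7 days comes first (3.1.2c), so it is at most about 112 − 7 = 105 days. No planned analysis names pre-enrolment prophylaxis duration.

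**4. Would follow-up correct the third row?** The visible CMF item asks about changes. A child recorded as stopped who simply continues has no change to report. The diary likewise collects changes (MOP 4.6, 7.4.2) or newly prescribed drugs (MOP 7.1).

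**5. Effect on the rule in 4.10.** It is worded for children who start prophylaxis. Applied literally to a child who continues from before enrolment, it would remove all of that child's follow-up. With the assigned stop date, all of that follow-up would be kept.

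**6. Possible size for Aim 1.** The benchmark is Table 8: one-sided alpha 0.05, power 80%, margin 0.10, ratio r = 360/150 = 2.4. At p = 0.15, n in group A = p(1 − p)(1 + 1/r)(1.645 + 0.842)² / 0.10² = 111.67, and the total is 111.67 × 3.4 = 379.69, rounded up to 380. This matches the plan.

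The documents give no prevalence of continued prophylaxis and no effect size for these children, so both are assumed. If a share f of CUTIE children continue unrecorded, with relative risk RR for scarring, the observed proportion is p(1 − f + f × RR).

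- If 5% to 20% of 360 are on prophylaxis at enrolment and half continue: 360 × 0.05 × 0.5 = 9 to 360 × 0.20 × 0.5 = 36 children, so f = 2.5% to 10%.
- With f = 10%, RR = 0.5, p = 15%: 0.90 × 15% + 0.10 × 7.5% = 14.25%, a shift of −0.75 points.
- Over a wider range, f = 5% to 30% and RR = 0.5 to 1.0, the shift is 0 to −2.25 points at p = 15%, 0 to −1.5 at 10% and 0 to −3.0 at 20%.

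The formula assumes that children who continue have the same underlying risk as the others. If prophylaxis were kept for those judged at higher risk, the net direction could differ.

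**The case against.** The strongest reply is that the sentence may do little harm. A child still on prophylaxis is also taking a current medication, which the baseline CMF records, and the unseen QxQ may say how to code it. Parents are asked to bring medicine bottles (MOP 4.5.2.1) and current medicines to clinic visits (MOP 7.2.3). Medication use is reviewed at each contact (MOP 7.1) and asked about again on the follow-up form (MOP 7.4.4.3). The CMF item comes from a screen that shows only part of the form, and MOP 14.4.8 says the electronic forms, unlike the paper ones, were not adapted to CUTIE. Every enrolled child has a VCUG without reflux, and Protocol 1.1.5 describes current care as prophylaxis only for those with reflux, so few may continue. The Synopsis and Protocol 1.1.2 cite placebo comparisons in which prophylaxis did not reduce scarring.

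Most of this stands, and it limits the consequence. It does not remove the defect. The listed routes might reveal continued use, but none cancels an explicit instruction to enter an assigned date, and which instruction prevails cannot be settled without the QxQ.

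A reader might infer that children who stay on prophylaxis are in fact analysed as untreated, giving a one-way bias that no analysis could detect. The documents do not support that. They do not show that any child continues, they do not say that the analysis takes exposure from this date, and they leave several ways for continued use to surface.

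**Conclusion.** The concern holds as a risk of misrecorded exposure. MOP 4.5.2.1 replaces an observed date with an assigned one, has no basis in a study without study medication, and does not fit with Protocol 1.1.3 and 4.10. Errors can go either way: continued use recorded as stopped, or earlier stopping recorded as exposure up to enrolment.

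The number of children affected and the net direction are unknown. Any effect on the Aim 1 difference is probably small: 0.75 points in the main illustration, nil if prophylaxis has no effect on scarring, and at most 3.0 points over the wider assumed range, against a margin of 10. These figures rest entirely on the assumed shares and relative risks. The case for change is that exposure should be verifiable and 4.10 applicable; it does not depend on a large expected bias.

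**What to change.** - Replace the sentence in MOP 4.5.2.1 with an instruction to record the actual stop date of any prophylactic antimicrobial taken since the index UTI, or to code it as continuing if it has not stopped. Align the QxQ.
- Confirm at each CMF contact whether the child is currently taking a prophylactic antimicrobial, as well as whether anything has changed. If the CUTIE paper form already asks this, nothing need be added.
- Reconcile MOP 4.5.2.1 with Protocol 4.10: classify children on prophylaxis at or after enrolment from observed dates, and handle those already on it by the same analysis rule as those who start later.

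The cost is one MOP/QxQ sentence, at most one question on an existing form and a clarifying sentence in 4.10. None of this bears on whether prophylaxis is given or stopped, which remains with the treating physician.
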